*Examining disparity driven vergence as a potential
diagnostic test for mild traumatic brain injury (mTBI)*

NCT Number NCT03529799

1) **Protocol Title**

Examining disparity driven vergence as a potential diagnostic test for mild traumatic brain injury (mTBI)

2) **IRB Review History***

None.

3) **Objectives***

Specific Aim 1 (SA1): Determine the validity and safety of disparity driven vergence testing with a portable goggle system using a pseudorandom ternary sequence of frequencies on a group of normal subjects.

Specific Aim 2 (SA2): Determine the vergence testing control values using a portable goggle system using a pseudorandom ternary sequence of frequencies on a group of normal subjects.

Specific Aim 3 (SA3): Determine the vergence testing values with a portable goggle system using a pseudorandom ternary sequence of frequencies on a group of subjects with history of mild traumatic brain injury and compare this to values in normal subjects.

4) **Background**

Vergence eye movements for focusing on objects include either convergence, the coordinated movement of both eyes towards the midline, or divergence, the coordination movement of both eyes towards the periphery. These eye movements are thought to be controlled by complex neurophysiological mechanisms that can be susceptible to damage by traumatic brain injury. Known involved areas in vergence include the oculomotor nucleus, cerebellum, and visual association cortex (Conn 2016), all of which can sustain damage during head trauma.

Modern balance function assessment includes electronystagmography and more recently, videonystagmography (ENG/VNG) to assess vertigo, dizziness, and imbalance. Additionally, vestibular-evoked myogenic potentials (VEMP), rotational testing, and computerized dynamic posturography (CDP) are very useful in evaluating multi-sensory integration of vision, somatosensory, and vestibular system function. VNG records eye movements using digital video image technology employing infrared illumination to determine eye position. The use of VNG enables simultaneous subjective observation of eye movements together with objective data collection and analysis of eye movement waveforms via computer algorithms (Kang 2015). More recently vestibular function has been tested in rotational chair devices. These devices utilize VNG goggles and perform many of the same tests done in a traditional VNG test but adds tests that involve moving the body (and with the body the head) through a variety of motion paradigms. Eye response to these body/head accelerations are recorded and abnormalities can be plotted against established norms. This technology is useful but involves a large and expensive piece of equipment in a dedicated vestibular lab. As a result, portable devices have been developed that perform many of the same functions that the chair performs. Head to head comparisons between rotational chair testing and portable vestibulo-ocular reflex gain and phase testing have shown consistent results between modalities (Goebel 1995). Portable vestibular testing has thus become a reality, allowing physicians

and audiologists the ability to test subjects outside of the typical clinical setting and in a variety of environments and conditions.

As such portable devices arise and become available to practitioners, their safety, validity, and efficacy must be determined. The portable goggle system, IPAS goggles (Neuro-kinectics, Inc., Pittsburgh, PA), have been developed to measure vestibular function and can be used for vergence testing. Current tests of binocular disparity driven vergence examine only one frequency (0.1 Hz) and tests at that single frequency may provide only limited information in the diagnosis and follow-up of mTBI patients. A greater number of frequencies can provide a spectrum of values that may help with this assessment. As testing all of the possible frequencies is not

feasible, we propose a pseudorandom ternary sequence approach to frequency distribution during disparity driven vergence to allow rapid analysis over a wide range of frequencies. Essentially, a pseudorandom frequency distribution can help extrapolate data to a larger frequency data set. We will also be evaluating the safety and side effect profile of using the goggles using a medical symptom questionnaire.

5) **Inclusion and Exclusion Criteria**

Inclusion:

- Aged 18 or older
- Both females and males

Exclusion:

- Central processing disorder
- Impaired vision without corrective lenses (max 20/60 uncorrected)
- Moderate to severe hearing loss (>55dB PTA, <50% word identification)
- Vestibular disorder except for patients recruited for SA3
- History of ear surgery other than myringotomy with or without tube placement
- Pregnant women
- Prisoners
- Adults unable to consent

6) **Number of Subjects**

60 subjects – 30 normal controls (no mTBI), 30 patients with mTBI.

7) **Recruitment Methods**

Normal subjects will be recruited from a pool of patients from a population who are unaffiliated or affiliated with University of Miami and meet inclusion criteria and not excluded by exclusion criteria. The faculty and students of any University of Miami School will be recruited through advertising in e-mails. Emails will be sent to staff and faculty associated with the UM Clinical Research Building (CRB) that have their emails stored in the UM Outlook server. Subjects will not be paid to participate. Students and staff will be assured that their participation will have no effect on their school performance or grades.

8) mTBI patients will be recruited by convenience from a pool of patients with history of mTBI and no prior vestibular disorders that present to the UM CRB Otology Clinic of [name] (SA3)”. The determination of their fitness for participation will be made during [name] clinical history and physical by asking about the history of the head injury and past medical history.

9) **Study Timelines**

Vestibular tests will take 15 minutes.

10) **Study Endpoints**

Each participant’s study will be completed when they have completed the vergence testing and other vestibular tests. At that point, the data will be de- identified.

11) **Procedures Involved**

The study will be conducted in 2 phases in which each phase comprises of thirty participants.

In the first phase, thirty participants without mTBI who meet the inclusion criteria and are not excluded will be chosen to participate. Participants will sign an informed consent document and undergo 1 session of vergence testing, along with a series of vestibular tests. After this testing, the data will be de-identified and will only be labeled with sex and age of patient.

In the second phase, thirty participants with mTBI who meet inclusion criteria and are not excluded will be chosen to participate. Participants will sign an informed consent document and undergo 1 session of vergence testing, along with a series of vestibular tests. After this testing the data will be de-identified and will only be labeled with sex and age of patient.

After the session, patients will be given a medical symptom/toxicity questionnaire (MSQ) to evaluate for any side effects.and the SCAT-5 questionnaire, which will evaluate their current symptoms.

For each vestibular test and data to be obtained, see table below:

Test	Activity	Outcome OR Ordinal Value
Vergence Pursuit	Focusing on object moving forward and backwards	0 - 100
Spontaneous Nystagmus	Focusing on an object	Normal / Abnormal (Side)
Saccades ~ Horizontal Random	Focusing on objects randomly in horizontal axis	Normal / Abnormal (Side)
Saccades ~ Vertical Random	Focusing on objects randomly in vertical axis	Normal / Abnormal (Side)
Smooth Pursuit Horizontal ~ 0.1 Hz	Tracking objects in horizontal axis, at 0.1 Hz	Normal / Abnormal (Side)
Smooth Pursuit Horizontal ~0.75 Hz	Tracking objects in horizontal axis, at 0.75 Hz	Normal / Abnormal (Side)
Smooth Pursuit Vertical ~0.1 Hz	Tracking objects in vertical axis, at 0.1 Hz	Normal / Abnormal (Side)

Smooth Pursuit Vertical ~0.75Hz	Tracking objects in vertical axis, at 0.75 Hz	Normal / Abnormal (Side)
Predictive Saccades	Tracking an object moving in predictable manner	Percent (%) Error
Antisaccade	Moving eyes away from visual onset	% Error
OKN (optokinetic nystagmus) Trapezoidal	Tracking moving field	Normal / Abnormal (Side)
Visual Reaction Time	Reaction time to object	Seconds
Saccades and Reaction Time	Reaction time to off-center object	Seconds
Auditory Reaction Time	Reaction time to sound	Seconds
Self-Paced Saccade	Saccadic motion between two fixed targets	0 - 100
Pupil Reflex	Normal light reflex	0 - 100
Subjective Visual Vertical	Ability to perceive subjective tilt	0 - 100

12) **Data Storage**

The only data to be stored will be the results of the vergence tests and vestibular testing done during the two sessions. These results will be tied together by a subject number that will also link to the sex of the patient and age of the patient. No PHI that identifies any participant will be kept. All the previously described data will be stored on the PI's computer and used for analyses purposes in room 580 of the clinical research building at the University of Miami Medical Center located at [name]. It will be password protected, and unique identifiers used for subject protection. Data will not be distributed, except in the form of peer-reviewed publication or oral presentation maintain the confidentiality of the subjects.

13) **Data Management***

Group mean data and single subject design will be utilized. In the group mean data scoring on each of the sessions will be aggregated for each of the specific aims. First session scores will be compared to second session scores using standard statistical methods with significance defined as $p < 0.05$. For the single subject design the number of subjects for each vestibular tests for each aim who have a significant difference in scores between the first and second session will be calculated and analyzed with descriptive statistics. In this way the investigators can calculate the difference between each test on the two sessions for each protocol, as it is very possible that some tests may be significantly different between the sessions and some tests will not.

Data will be stored on the PI's computer and used for analyses purposes in room 580 of the clinical research building at the University of Miami Medical Center located at [name]. It will be password protected, and unique identifiers used for subject protection. Data will not be distributed, except in the form of peer-reviewed publication or oral presentation maintain the confidentiality of the subjects. . No PHI that can identify any subjects will be kept beyond the second session of testing.

14) **Withdrawal of Subjects**

Subjects can withdraw at any time but if they withdraw their data will not be used and they will be replaced in the study by a new subject.

15) **Risks to Subjects**

The risks to the subjects will be minimal. At most, a breach of confidentiality composes the majority of the risk. We will take extensive measures to protect confidentiality and to ensure data security.

16) **Potential Benefits to Subjects**

Participating in this protocol has no potential benefit to the patients.

17) **Vulnerable Populations**

This research does not involve any venerable populations.

18) **Sharing of Results with Subjects**

Subjects can see the results of their testing after each session and can see the overall study outcome when it is prepared for scholarly presentation and publication.

19) **Setting**

All testing will take place in the University of Miami Ear and Hearing Center in the Clinical Research Building fifth floor and at a designated site on the University of Miami main campus.

20) **Resources Available**

A pair of testing goggles pre-programed to perform the test battery will be available to the investigator.

21) **Prior Approvals**

None however these same testing goggles have been used in at least two previously approved protocols at the University of Miami.

22) **Confidentiality**

We will take exhaustive measures to protect confidentiality at all times. Patients will be assigned unique identifier codes and the code will be stored separately from the subject's records. The records will be stored in a locked file in the office of PI-[name]. All computers used in the research will have strong password protection and the data will be accessible only to authorized research personnel. Data will be stored pursuant to time frames listed under "How Long Do I Keep Research Records" in the Investigator's Manual.

23) **Provisions to Protect the Privacy Interests of Subjects**

Subjects will be identified by an alphanumeric code designed to prevent disclosure of their identity. Information may be stored in an electronic database which will be secured with a password known only to the PI involved in this study. The database will be kept electronically until the conclusion of the study, at which time it will be printed and placed in a secure file with all other materials relevant to the study. We

will not be accessed any Protected Health Information prior to contact the subject in the clinic and neither will be accessed during the course of the proposed research, no medical record required , we will collect only name, and DOB

24) **Compensation for Research-Related Injury**

None anticipated since this is not more than minimal risk.

25) **Economic Burden to Subjects**

None anticipated.

26) **Consent Process**

Consent will be obtained by the PI, Sub-I, or study coordinator in the Ear Clinic at the University of Miami Medical Center any participants who wish to enroll in the study will be consented at the ENT clinic prior to initiating any study procedures. Informed consent will be obtained in writing via the attached documents. Participants will be taken into a private room to read the consent form and have any questions regarding the study answered by a research team member.

Waiver or Alteration of Consent Process (consent will not be obtained, required information will not be disclosed, or the research involves deception)

No Waiver being sought

Subjects who are not yet adults (infants, children, teenagers)

Not part of subject population

Cognitively Impaired Adults

Not part of subject population

Adults Unable to Consent

Not included in subject population

References

Conn PM. "Vision." *Conn's Translational Neuroscience*. San Diego: Academic Press, 2017. 399-438.

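### The study poses a diagnostic question, but section 13 plans no measure of how well vergence separates mTBI patients from normals

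*Combined protocol and SAP*

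**What the plan says.** The title frames the study as "Examining disparity driven vergence as a potential diagnostic test for mild traumatic brain injury (mTBI". Section 4 (Background) justifies the multi-frequency sequence partly by the limited diagnostic information from a single frequency. In section 3 (Objectives), SA2 sets control values in normals. SA3 obtains vergence values "on a group of subjects with history of mild traumatic brain injury and compare this to values in normal subjects". Section 6 gives the size as "60 subjects – 30 normal controls (no mTBI), 30 patients with mTBI", without power, effect size or target accuracy.

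Section 13 (Data Management) is the whole analysis plan and has two parts:

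- **Group means.** "First session scores will be compared to second session scores", and this is done "using standard statistical methods with significance defined as" p<0.05.
- **Single-subject design.** For each test, the number of subjects whose scores differ significantly between the two sessions is counted and described.

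Section 11 says that participants in each phase "undergo 1 session of vergence testing, along with a series of vestibular tests". Its table lists the vergence outcome only as a 0 to 100 value, with no SD, abnormal direction or cut-off.

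**The concern.** A diagnostic question is about individuals: given a vergence result, how well can one tell an mTBI patient from a normal subject? A test of means answers whether the two averages differ. Two distributions can have clearly different means and still overlap so much that many subjects fall on the wrong side of any cut-off.

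Nothing in section 13 measures that overlap, and nothing turns the SA2 control values into a rule for a positive or negative vergence result. The single-subject count does not fill the gap, because it counts changes between sessions and not correct classifications. The between-session wording adds a second problem: read literally, the plan specifies no mTBI v normal analysis for SA3 at all.

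The risk is that a significant p-value is reported as support for a diagnostic test when the same data, summarised as accuracy, would show weak separation with a lower confidence limit near chance.

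**Working it through.** The plan gives no power or accuracy figure to reproduce. The check asks what a just-significant comparison of means would imply for discrimination.

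**Inputs.** n = 30 per group (section 6); alpha = 0.05 (section 13). Assumed, because the documents do not say: the test is two-sided, it compares mTBI with normals, and scores are normal with equal variance.

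**1. Smallest significant observed difference.** d = t(0.975, 58 df) × √(2/30) = 2.002 × 0.258 = 0.517 SD. A one-sided test would give 0.432 SD.

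**2. Discrimination at that difference.**

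- AUC = Φ(d/√2) = Φ(0.365) = 0.643.
- Sensitivity = specificity at the midpoint cut-off = Φ(d/2) = Φ(0.258) = 0.602, so about 40% of each group is misclassified.
- Positive likelihood ratio = 0.602/0.398 = 1.51.
- Sensitivity at 90% specificity = Φ(0.517 − 1.282) = 0.22.
- Sensitivity at 95% specificity = Φ(0.517 − 1.645) = 0.13.
- One-sided test: AUC 0.62, sensitivity = specificity 0.59.

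**3. Precision of that AUC (Hanley-McNeil).** With A = 0.643, a = A/(2 − A) = 0.474 and b = 2A²/(1 + A) = 0.503:

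SE = √{[A(1 − A) + 29(a − A²) + 29(b − A²)]/900} = √(4.586/900) = 0.071.

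95% CI = 0.643 ± 1.96 × 0.071 = 0.50 to 0.78.

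**4. Chance of significance for given true differences (noncentral t).**

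| True d | AUC | Sensitivity = specificity | Power |
|---|---|---|---|
| 0.20 | 0.56 | 54% | 12% |
| 0.50 | 0.64 | 60% | 48% |
| 0.74 | 0.70 | 64% | 80% |

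Even a true difference that this size detects with about 80% power leaves about 36% of each group misclassified.

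**5. Precision if accuracy were reported instead.** The observed values here are illustrative, since the documents give none.

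- AUC 0.70: SE 0.068, 95% CI 0.57 to 0.83.
- AUC 0.80: 95% CI 0.69 to 0.91.
- Sensitivity 24/30 (80%): exact 95% CI 61% to 92%.

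**6. Precision of a limit taken from 30 normals.** The 95% half-width is 1.96 × √(1/30 + z²/58) SD.

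- 5th percentile (z = 1.645): 1.96 × √(0.0333 + 0.0467) = 0.55 SD.
- 2.5th percentile (z = 1.96): 1.96 × √(0.0333 + 0.0662) = 0.62 SD.

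**The case against.** The strongest reply is that this is an early study. The title says only that the test is potential, no aim promises accuracy estimates, and a comparison of group values is a legitimate first step with 30 + 30 subjects and convenience-recruited patients. That stands as an argument about ambition, and it makes the gap less severe. It does not remove the gap: an early study still needs an estimate that bears on its question, and an AUC with its interval shows how preliminary the answer is in a way that a p-value does not. Whether the AUC replaces or accompanies the mean comparison is secondary.

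A second reply is that sessions in section 13 may mean the two phases, so that the test is really mTBI against normals. The single-subject analysis speaks against this, because it needs two scores from one person. Even on the generous reading the test is still one of means, which is the case worked through above.

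A third reply is that the accuracy figures depend on equal-variance normality for a 0 to 100 score of unknown SD, and describe the borderline case; other significant results would show larger differences. Both points are fair, and the figures should be read that way.

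A fourth is that the protocol names no primary vergence variable and no abnormal direction, so an ROC analysis cannot simply be written in. This is correct and is part of the fix.

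A reader might also infer that a significant result could come from a test with almost no diagnostic value. The figures do not support that at this size. Significance needs an observed AUC of about 0.64, which is poor but not nil; only its lower confidence limit is close to chance. A true difference of 0.2 SD would reach significance only 12% of the time.

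**Conclusion.** The point holds as an avoidable gap that should be closed. The question is diagnostic, and neither analysis in section 13 measures discrimination. If SA3 is tested as a two-sided comparison of means in 30 v 30 under equal-variance normality, the threshold for p<0.05 sits at an observed 0.52 SD. That is an AUC of about 0.64 (95% CI about 0.50 to 0.78) with about 60% sensitivity and specificity.

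It would go too far to say that the plan contains only an mTBI v normal test of means. The written test is between sessions, the group test is unspecified, and a descriptive count is also planned. Nor do the documents show that vergence is a poor test, because they contain no data. The conclusion is limited to this: the plan as written cannot say how well vergence separates individuals, and a significant p-value would not reveal poor separation.

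**What to change.** In section 13:

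- Replace the between-session wording for SA3 with an mTBI v normal comparison, and reconcile sections 11, 12 and 13 on the number of sessions.
- Name one vergence variable and its direction of abnormality before the data are seen.
- Report its ROC area with a 95% CI and the mean difference with a 95% CI.
- Report sensitivity with an exact 95% CI at one pre-set limit derived from the SA2 normals, for example a 5th-percentile limit if low values are the abnormal ones. Do not choose the cut-off to fit the mTBI data.
- Give that limit its own CI, and state that specificity in the same normals is fixed by construction and is not an independent estimate.
- Limit the conclusion to preliminary discrimination between these normals and clinic mTBI patients.

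The cost is a rewritten analysis section and an advance decision on one variable and its direction; no extra subjects, visits or measurements are needed. The drawback is that the intervals will be visibly wide and will look less favourable than a p-value.

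### SA1 promises to determine validity in normal subjects, but the plan cannot show it on either reading of its session count

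*Combined protocol and SAP*

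**What the plan says.** Section 3, SA1, sets out to "Determine the validity and safety of disparity driven vergence testing with a portable goggle system using a pseudorandom ternary sequence" on a group of normal subjects. Section 6 fixes the groups at "30 normal controls (no mTBI), 30 patients with mTBI".

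The sections disagree on how many times each person is tested:

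- Section 11 (Procedures Involved): participants in each phase "undergo 1 session of vergence testing, along with a series of vestibular tests".
- Section 12 (Data Storage): the stored data are the "results of the vergence tests and vestibular testing done during the two sessions".
- Section 13 (Data Management): "scoring on each of the sessions will be aggregated for each of the specific aims", and "First session scores will be compared to second session scores using standard statistical methods", with significance at p < 0.05. It adds a descriptive count of subjects whose scores differ significantly between sessions.

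On a possible reference, the Background (section 4) says "Current tests of binocular disparity driven vergence examine only one frequency (0.1 Hz"), and gives this as the reason for a multi-frequency sequence. The section 11 table has one vergence item, Vergence Pursuit, scored 0 to 100. It is not labelled as either the new test or a comparator.

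**The concern.** Validity is half of the first aim, and the Background treats it as something that must be established for portable devices. To support the word, a plan needs some evidence that the score measures what it should: a comparison with an accepted measurement, a contrast between groups expected to differ, or another stated criterion. Repeatability is not validity, but it is a precondition for it. SA1 designates none of these.

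At stake is what the study may conclude. SA2 sets control values and SA3 compares mTBI patients with those controls. Both can be estimated whatever SA1 is called. But if SA1 is taken as achieved once the normal subjects have been tested, the later results will appear to rest on a measure already shown to be valid. A second hazard lies in section 13: a non-significant session difference could be read as evidence that the test is repeatable.

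**Working it through.** **The plan's own figure.** The only sample-size figure is 30 + 30 = 60, which agrees with section 6. No power, effect size, standard deviation, precision target or agreement limit is given, so there is no derivation to reproduce.

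**Inputs.** n = 30 normal subjects (section 6); significance level 0.05 (section 13), taken as two-sided because the sidedness is not stated. The ICC values and the mean shift below are assumptions for illustration.

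**Reading 1: one session (section 11).** Each subject has one score. Within-subject variance cannot be separated from between-subject variance, so no repeatability statistic can be computed.

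**Reading 2: two sessions (sections 12 and 13).** Section 13 names no test; a paired t-test is assumed. Let a score have total SD σ and between-session correlation ICC.

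- SD of the differences = σ√(2(1 − ICC)).
- t = mean difference ÷ (SD of differences/√30), on 29 df, critical value 2.045.

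With no mean shift, t has the same null distribution whatever the ICC. Simulation with 40,000 runs per case shows this in the middle column. The last column adds a true shift of 0.25σ.

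| Assumed ICC | SD of differences | Non-significant, no shift | Non-significant, shift 0.25σ |
|---|---|---|---|
| 0 | 1.41σ | 95.0% | 84% |
| 0.3 | 1.18σ | 95.0% | 80% |
| 0.6 | 0.89σ | 95.0% | 68% |
| 0.9 | 0.45σ | 95.1% | 16% |

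A score that is pure noise passes the no-shift check as often as a highly repeatable one. With a shift, the noisier measure is the more likely to look unchanged. By the noncentral t distribution, the test has 80% power only for a mean shift of 0.53 SD of the differences, and 90% for 0.61. The per-subject count does not help as written, because section 13 gives no rule for when one subject's change is significant.

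**What two sessions could give if analysed for agreement.** For a one-way ICC r with two sessions, F = (1 + r)/(1 − r) on 29 and 30 df. The bounds are (F_L − 1)/(F_L + 1) and (F_U − 1)/(F_U + 1), where F_L = F/F₀.₉₇₅(29, 30) and F_U = F × F₀.₉₇₅(30, 29).

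- For r = 0.8: F = 1.8/0.2 = 9; F_L = 9/2.083 = 4.32; F_U = 9 × 2.092 = 18.83. The interval is 3.32/5.32 = 0.62 to 17.83/19.83 = 0.90.
- In the same way, r = 0.6 gives 0.32 to 0.79, and r = 0.9 gives 0.80 to 0.95.
- Each Bland-Altman limit has a 95% CI half-width of 2.045 × √(1/30 + 1.96²/(2 × 29)) = 2.045 × 0.3155 = 0.65 SD of the differences.

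**Reference measurement, either reading.** The 0.1 Hz vergence test appears only in the Background. So does the rotational chair, which is cited there for head-to-head comparisons of portable vestibulo-ocular reflex testing. Neither is carried into section 11 or 13 as a comparator.

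**The case against.** The strongest reply is section 13. It plans a between-session comparison for every aim, SA1 included, and section 12 refers to two sessions. A reader who looked only at section 11 might infer that every normal subject is tested once and that the protocol contains no between-session analysis at all. The documents do not support that: on sections 12 and 13, all 30 could have a repeat measurement. What stands of the reply is that the session count is unresolved. It does not rescue SA1, because a difference test does not measure agreement and no reference is named.

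A second reply is that SA3 could supply known-groups evidence. That is fair, so it would be too strong to say that nothing in the study could bear on validity. But SA1 is confined to normal subjects, and the plan does not link SA3 to validity.

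A third is that Vergence Pursuit could serve as a same-session comparator. The table does not say what it represents. As the only vergence item, it may itself be the new test.

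Two further inferences should be resisted. The safety half of SA1 is not undermined here: it has a data source in the symptom questionnaire (MSQ) given after testing. Nor does the protocol say that completing the sessions will be reported as proof of validity.

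**Conclusion.** The point holds in this form: SA1 names a property that the plan, as written, cannot establish. With one session, repeatability is not estimable. With two, the planned comparison is non-significant about 95% of the time at any ICC when there is no mean shift, so it cannot tell a useless measure from a reliable one. On both readings there is no designated reference measurement, agreement statistic or validity criterion.

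The figures rest on n = 30, a two-sided paired t-test, normally distributed scores and assumed ICCs. The conclusion about the missing reference and criterion rests on the text alone. Sections 11, 12 and 13 contradict each other on the number of sessions; which is intended cannot be settled from the documents.

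**What to change.** First reconcile section 11 with sections 12 and 13 on the number of sessions. Then:

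(a) **If there is one session**, remove validity from SA1 and from the conclusions. Restate SA1 as feasibility and tolerability in normal subjects.

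- Feasibility: the proportion of all normal subjects who start testing and yield an analysable recording, with an exact 95% CI. Section 14 discards the data of those who withdraw and replaces them, so they must still be counted in this denominator; otherwise the proportion is biased towards success.
- Tolerability: the MSQ results.
- Describe any separation found under SA3 as preliminary known-groups evidence only.

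(b) **If two sessions are in fact held**, replace the section 13 difference test for SA1 with an ICC and Bland-Altman limits of agreement, each with a 95% CI. Call the result repeatability, not validity.

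The cost is a more modest claim and a little more analysis. Neither route adds a session, a device or a participant.

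### A 20/60 acuity limit is the only visual entry criterion, so people with a long-standing lack of binocular fusion can enter either group of a binocular vergence study and can distort SA2 and SA3

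*Combined protocol and SAP*

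**What the plan says.** The measurement needs two working eyes. Section 4 describes "convergence, the coordinated movement of both eyes towards the midline" and notes that "Current tests of binocular disparity driven vergence examine only one frequency (0.1 Hz"). It then says "we propose a pseudorandom ternary sequence approach to frequency distribution during disparity driven vergence".

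SA2 is to "Determine the vergence testing control values using a portable goggle system" in normal subjects. SA3 is to obtain values in "subjects with history of mild traumatic brain injury and compare this to values in normal subjects". Section 6 sets the numbers: "30 normal controls (no mTBI), 30 patients with mTBI".

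Section 5 lists two inclusion items (adult age, either sex) and eight exclusions. Only one exclusion concerns vision: "Impaired vision without corrective lenses (max 20/60 uncorrected"). The nearest other item, "Central processing disorder", is not defined.

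Section 7 recruits controls by e-mail under the same criteria and describes no interview. Section 8 judges the fitness of mTBI patients at a clinical history and physical that covers the head injury and earlier medical problems; no eye question is named. No test in the Section 11 table is described as a check of alignment, fusion or stereopsis. Sections 11 and 12 keep the test results with age and sex only.

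**The concern.** A response driven by binocular disparity presupposes that the subject can fuse the two images. Visual acuity is a different property. Someone with long-standing strabismus can read 20/20 with each eye and still lack fusion, so that person passes Section 5 on any reading of the acuity rule. Section 5 does screen for hearing loss and ear surgery, yet leaves out the sensory defect closest to the endpoint.

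Each aim is exposed:

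- **SA1:** a failed response could reflect the goggles or the subject.
- **SA2:** an affected control can pull down the mean and inflate the spread of the control values.
- **SA3:** those values are the comparator, and a lifelong defect in an mTBI patient could be read as an effect of injury.

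The problem cannot be repaired in the analysis. No eye history is collected, so a lifelong non-fuser looks the same in the data as a genuinely poor responder. Section 22 mentions a code held separately, but there is no ocular record for it to link to.

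**Working it through.** The plan gives no power, effect size, SD or normal limit, so there is no figure of its own to reproduce. What follows is an illustration.

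**From the documents:** 30 controls and 30 mTBI patients (Section 6); significance at 0.05 (Section 13; two-sided assumed).

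**Assumed:** prevalence p of the defect among otherwise eligible adults, 1% to 5%; an affected person scores D = 2 to 4 SD below the rest; lower is worse and mTBI lowers the score; comparison of two means by normal approximation; a lower limit of mean − 1.96 SD, for illustration only.

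**Step 1. Chance of enrolling at least one affected person:** 1 − (1 − p)^n.

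| p | among 30 controls | among all 60 |
|---|---|---|
| 1% | 26% | 45% |
| 3% | 60% | 84% |
| 5% | 79% | 95% |

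**Step 2. Effect of one affected control on the SA2 values.** With q = 1/30 and the unaffected group at mean 0 and SD 1, the mean shift is −qD and the SD is √(1 + q(1 − q)D²), where q(1 − q) = 0.0322.

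- D = 2: mean −0.067; SD √(1 + 0.129) = 1.062; limit −0.067 − 1.96 × 1.062 = −2.15.
- D = 4: mean −0.133; SD √(1 + 0.516) = 1.231; limit −0.133 − 1.96 × 1.231 = −2.55.

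With no affected control the limit is −1.96. The SD therefore rises by about 6% to 23%.

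**Step 3. Effect on SA3.** With 30 clean subjects per group, the difference detectable at 80% power is (1.96 + 0.84) × √(2/30) = 0.72 SD (0.724 is used below). Power is Φ(difference/SE − 1.96).

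One affected control, none in the mTBI group (SE = √((SD² + 1)/30)):

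- D = 2: (0.724 − 0.067)/0.266 − 1.96 = 0.51, power 69%.
- D = 4: (0.724 − 0.133)/0.290 − 1.96 = 0.08, power 53%.

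One affected in each group (SE = √(2·SD²/30); the mean shifts cancel):

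- D = 2: 0.724/0.274 − 1.96 = 0.68, power 75%.
- D = 4: 0.724/0.318 − 1.96 = 0.32, power about 63% (0.625).

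Affected subjects in the mTBI group only, with no true difference: the false-positive rate rises from 5% to about 6% to 8% with one affected, and to about 8% to 14% with two.

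**The case against.** The strongest reply is that the size of the harm is assumed. At 1% prevalence there is a 74% chance that no affected control enrols, and then nothing is distorted. That stands: the plan can distort the results, not that it must.

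Three stronger readings are tempting, and the documents do not support them.

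- **A non-fusing control scores near zero and wrecks the normal range.** On the 0–100 scale in the Section 11 table, adding a score of 0 to 29 controls with an assumed mean of 70 and SD of 10 would drop the lower limit from 50.4 to 36.1. But that score is 7 SD below the mean. The table attaches the scale to a vergence pursuit task and does not say that it is the pseudorandom disparity score, or what a non-fuser would obtain. Nor does the protocol define a normal limit, so it cannot be said that abnormal patients would be classed as normal.
- **The SA3 contrast is systematically biased.** If pre-existing defects are equally common in both groups, the expected difference in means is not shifted by them. The cost is then mainly power, plus chance imbalance in any one sample of 30 per group.
- **A person with 20/20 in one eye and 20/200 in the other is eligible.** That holds only if acuity is tested with both eyes open. A per-eye reading is equally open and would exclude that person. It would not exclude strabismus with good acuity in each eye, so the gap remains on either reading.

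It can also be said that the Section 8 history and physical gives a chance to detect known defects. It does, but only in mTBI patients, and no criterion tells the examiner to act on what is found. Finally, broader controls are arguable for a possible diagnostic test. That would be a reasonable deliberate choice, but the protocol does not state it and records nothing that would let the affected subjects be described.

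**Conclusion.** The concern holds as a gap in eligibility with a probable, not certain, effect. The textual part is firm: acuity is the only visual criterion, nothing screens for fusion, and the stored data cannot identify affected people afterwards. The size is conditional on the assumptions above. At 1% to 5% prevalence, the chance of at least one affected control is 26% to 79%. With one such control 2 to 4 SD low, the illustrative limit moves from −1.96 to between −2.15 and −2.55 SD, and power for a 0.72 SD difference falls from 80% to 69–53%, or to 75–63% with one affected in each group. With 30 per group this is enough to justify a cheap change before enrolment. It does not show that the results would be invalid.

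**What to change.** Amend Section 5, for both groups, to exclude known strabismus, amblyopia, monocular vision or absent binocular fusion that is long-standing or, in mTBI patients, predates the head injury. State that vergence problems that began with the injury remain eligible in the mTBI group, since they are part of what SA3 looks for. State that the 20/60 limit applies to each eye.

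Ask the history questions at the Section 8 clinical history for mTBI patients, and at the consent visit for controls, for whom no interview is now described.

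The cost is amendment wording, a few questions and a new screening step for controls. A few volunteers will be turned away, history will miss defects that people do not know they have, and the control values will apply to people with normal binocular vision.
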